#### 11.3.4 Other Medication

All concurrent treatment or medications given within 30 days prior to Randomization and until Visit 10/EoS, will be recorded in the CRF.

The use of any inhaled formulation of Cyclosporine A other than the IMP is strictly prohibited during the complete clinical trial period. Topical formulations (e.g., eye drops) containing CsA are allowed. Patients should not receive systemic Cyclosporine A at any time during Screening and Randomization. If medically indicated after Randomization, the treating physician can exchange Tacrolimus for systemic Cyclosporine A.

All inhaled medications, except investigational inhaled medications, are permissible during the trial and should be administered in the following order: inhaled bronchodilators, inhaled corticosteroids, inhaled antifungals/antibiotics, and then inhaled L-CsA. Spirometry must be performed without the use of bronchodilators (see Section 12.1.1.1) and preferably before but at least 2 hours after the last administration of inhaled antifungals/antibiotics.

To standardize spirometry across the two treatment arms, patients should not use short-acting bronchodilators (e.g., albuterol) 2 hours prior to spirometry. Patients on scheduled Long-Acting Beta Agonists (LABAs) or Long-Acting Muscarinic Antagonists (LAMAs) should ideally have spirometry done at the same time of day following their scheduled dose. Patients have to note their use and timing of bronchodilators carefully.

Protocol Number:

Sponsor:

L-CsA:

The reason for non-compliance shall be documented accordingly on the respective CRF.

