# 12 Immunosuppressants

Immunosuppressants are collected in the Concomitant Medications CRF form.

As per CRF completion guidelines, immunosuppressants are to be collected using the same measurement unit i.e., mg. In those cases where it is not done, considerations will be taken on ongoing basis (at DRM at the latest) to convert units for each immunosuppressive agent to allow cumulative dose to be calculated. Immunosuppressant medications will be coded using the World Health Organization (WHO-DD) classification system and grouped by drug class and PT.

In order to identify immunosuppressants among concomitant medications, any of the following two rules will be applied.

1. Only the following routes are to be considered: oral, intramuscular, intravenous, and subcutaneous;

the following codes are to be considered:

- o L04A Immunosuppressants:
  - 1. L04AA Selective immunosuppressants,
  - 2. L04AB Tumor necrosis factor alpha (TNF- $\alpha$ ) inhibitors,
  - 3. L04AC Interleukin inhibitors,
  - 4. L04AD Calcineurin inhibitors,
  - 5. L04AX Other immunosuppressants;
- o H02AB Glucocorticoids (all);

Final Version 5.0 Page 35 of 76

L04AD02 Tacrolimus, and route = sublingual.

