### 12.1 Basic Immunosuppressants

As per protocol, regardless of treatment assignment, all clinical trial participants must be on a maintenance regimen of immunosuppressive agents including tacrolimus, a second agent such as but not limited to mycophenolate motfetil (MMF) or azathioprine, and a systemic corticosteroid such as prednisone as third agent. At each visit, the average maintenance doses of immunosuppressive agents will be recorded by the Investigator on the Concomitant Medication eCRF.

Basic immunosuppressants refer to maintenance regimen of immunosuppressive agents and include the following:

- Calcineurin inhibitors (Tacrolimus, Cyclosporine A);
- Antimetabolicte (Antimetabolite) agents (MMF, Azathioprine);
- mTOR inhibitor (Everolimus, Sirolimus);
- Selective costimulation blocker (Belatacept);
- Corticosteroids.

The total basic immunosuppression administered from the day of randomization will be evaluated.

Basic immunosuppressives will be coded by Anatomical Therapeutic Code (ATC) codes, and will be summarized by treatment group for SAF, FAS and PPS.

A p-value will be obtained from the Fisher's Exact test for the comparison of patients with any basic immunosuppressants from L-CsA plus SoC versus patients with any basic immunosuppressants from SoC alone, for each class of basic immunosuppressants listed above.

Descriptive statistics on cumulative doses for basic immunosuppressants will be provided:

- for the whole treatment period (from day of randomization to end of study),
- for each period between study visits (V1 to V2, V2 to V3, etc.),
- cumulatively for each period between study visits (V1 to V2, V1 to V3, V1 to V4, etc.),

where periods between study visits  $V_i$  to  $V_{i+1}$  (with i=2,3,4, etc) is defined as the interval starting from the first day post visit  $V_i$  and ending the last day of visit  $V_{i+1}$  (included). For V1 to V2 the date of V1 must be considered too.

Final Version 5.0 Page 36 of 76

Descriptive statistics will be calculated for each class of basic immunosuppressants listed above and overall. If a patient took more than one basic immunosuppressant related to the same class, then the total dose will be taken into consideration in the calculation.

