P-values will be obtained from the Fisher's Exact test for the comparison of patients with any basic immunosuppressants, including each of basic immunosuppressant listed above from L-CsA plus SoC versus patients with any basic immunosuppressants from SoC alone at each time interval (V1 to V2, V1 to V3, ...., V1 to V9).

Exposure to immunosuppressant medication details will be summarized similarly for each category of basic immunosuppressant, and overall for all.

This includes the calculation of the duration of intake (date of last basic immunosuppressant intake - date of first basic immunosuppressant intake + 1). The duration will be calculated by summing the duration of the associated treatments. The overlapping days will be counted only once.

The ratio between the cumulative dose and intake duration will be used to produce the dose per day. The overall dose per day per patient will then be displayed for each treatment group for each time interval along with the 95% confidence interval.

By-patient listings will be provided for all basic immunosuppressants for FAS.

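### Cumulative immunosuppressant dose is summed in raw mg across different drugs, so the overall row and the mixed-class rows cannot support the planned between-group comparison

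*SAP*

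**What the plan says.** SAP section 12 sets the unit: "As per CRF completion guidelines, immunosuppressants are to be collected using the same measurement unit i.e., mg". Where another unit was used, the plan is "to convert units for each immunosuppressive agent to allow cumulative dose to be calculated". That is a change of unit, not of potency.

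SAP 12.1 lists five classes: calcineurin inhibitors (tacrolimus, cyclosporine A), antimetabolites (MMF, azathioprine), mTOR inhibitors (everolimus, sirolimus), belatacept and corticosteroids. On cumulative dose it says: "Descriptive statistics will be calculated for each class of basic immunosuppressants listed above and overall". For a patient with more than one drug of a class, "then the total dose will be taken into consideration in the calculation". Dose per day is cumulative dose divided by intake duration, and "The overall dose per day per patient will then be displayed for each treatment group", with a 95% confidence interval. SAP 12.2 applies the same dose and exposure statistics to all other immunosuppressants.

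The protocol synopsis describes the measure differently: cumulative dose for tacrolimus, for MMF or an equivalent, and for corticosteroids. Protocol 15.2.4 promises a descriptive comparison of cumulative maintenance dose between the groups. Protocol 11.3.4 allows a switch within a class after randomization, when medically indicated: "the treating physician can exchange Tacrolimus for systemic Cyclosporine A".

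**The concern.** A sum of mg measures exposure only if a mg means the same thing for every drug in it. The classes in SAP 12.1 combine different agents, and section 12 admits all systemic glucocorticoids by several routes. Nothing in the visible text puts them on a common scale.

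The comparison matters because treating physicians and patients know the allocation, changes to standard of care are at the investigator's discretion, and FEV1 measured after such changes stays in the primary analysis. A reader of the study report will look to these tables to see whether background therapy ran alike in the two arms. Two arms could differ in tacrolimus or steroid intensity and show the same overall total. They could also be treated with equal intensity and show different totals because a few patients took a different drug of the same class.

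**Working it through.** The plan gives no figure to reproduce here, so the check is arithmetic on the summing rule. The documents give no typical daily doses. The following are **assumptions for illustration**, in mg/day (low / mid / high): tacrolimus 2 / 4 / 10; cyclosporine A 100 / 200 / 400; MMF 1000 / 2000 / 3000; azathioprine 50 / 100 / 150; prednisone 5 / 7.5 / 20. SAP 8.2 reports 169 patients randomized; at 1:1 that is about 85 per arm (169/2 = 84.5).

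**Overall row**, patient on tacrolimus, MMF and prednisone. Mid total = 4 + 2000 + 7.5 = 2011.5 mg/day.
- MMF share: 2000/2011.5 = 99.4%. Lowest 1000/1030 = 97.1%; highest 3000/3007 = 99.8%.
- 30% cut in tacrolimus: 0.3 × 4/2011.5 = 0.06% of the total. Range 0.6/3022 = 0.02% to 3/1015 = 0.30%.
- Tacrolimus and prednisone both doubled: 11.5/2011.5 = +0.6%.
- MMF replaced by azathioprine: (2000 − 100)/2011.5 = −94%. Range −83% (850/1030) to −98% (2950/3007).

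**Calcineurin row.** If a share s of an arm switches to a drug with r times the mg, the class mean is multiplied by 1 + s(r − 1).
- One patient of 85 switched for the whole period, 4 to 200 mg: (200 − 4)/85 = +2.3 mg/day, or +58% on a mean of 4. Range +11% (10 to 100 mg) to +234% (2 to 400 mg). A switch part-way through counts in proportion to the time remaining.
- A 30% tacrolimus cut in every patient of the arm: −1.2 mg/day.
- Switching share that would hide that cut: s = 0.3t/(c − 0.7t), with t and c the tacrolimus and cyclosporine doses. At mid doses 1.2/197.2 = 0.6%; range 0.15% (0.6/398.6) to 3.2% (3/93). At mid doses that is less than one patient in 85.

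**Antimetabolite row.** Assume 20% of patients on azathioprine: mean = 0.8 × 2000 + 0.2 × 100 = 1620 mg/day. Ten points more azathioprine users: −0.1 × 1900 = −190 mg/day, or −12% (range −10% to −12%), with no change in any drug's own dose.

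The mTOR and corticosteroid rows follow the same algebra but were not quantified.

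**The case against.** The other side has a good deal to say.

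- **These are descriptive tables.** No test or decision rule uses them. Changes of background therapy after randomization are kept in the primary analysis by design.
- **Other outputs carry drug-level information.** Protocol 13.1.5.2 and SAP 15.5.2 cover calcineurin-inhibitor trough levels, and the latter mTOR levels too, by arm. SAP 12.1 and 12.2 give ATC summaries. SAP 12.1 adds by-patient listings of basic immunosuppressants. SAP 14.3.5 summarizes time to additional immunosuppression and points to 14.5.1, which is redacted. This stands as partial cover. Trough levels say nothing about MMF, azathioprine or steroids, and no visible output compares within-class switches or dose increases by arm.
- **Some rows are sound.** Belatacept is a single drug. Patients should enter on tacrolimus, systemic cyclosporine is barred around screening and randomization, and the protocol asks that drug types be kept. The calcineurin row is therefore a tacrolimus row except for later switches.
- **The protocol itself speaks of classes.** Section 15.2.4 names drug classes, and the synopsis wording on MMF can mean an equivalent drug as well as an equivalent dose. So the departure from the synopsis is less sharp than it first looks, but neither text calls for one mg total over all classes.
- **The doses are assumed.** This is true, and the exact percentages depend on them. The mechanism does not.

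A reader might infer that the Fisher tests are empty because eligibility puts everyone on immunosuppressants: "A p-value will be obtained from the Fisher's Exact test for the comparison of patients with any basic immunosuppressants". The sentence goes on to specify one test per class. Such a test says little for calcineurin inhibitors and corticosteroids, where use should be near 100% in both arms. It can be informative for mTOR inhibitors and belatacept, which eligibility does not require, and protocol 11.3.1 names an mTOR inhibitor as a possible fourth drug. The tests should stay.

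**Conclusion.** The summing rule is wrong as written, for a descriptive output. The overall row is in effect an MMF table (97.1% to 99.8% of the total under the assumed doses) and barely registers a change in tacrolimus or steroid dose. Mixed-class rows can move with drug choice alone. These rows, and the dose-per-day figures and confidence intervals built on them, cannot support the comparison promised in protocol 15.2.4.

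Two stronger readings are tempting and not supported. One is that this table is the trial's designated check that an FEV1 difference is not due to unequal background therapy. No passage says so; protocol 9.2 argues low bias partly from background therapy not needing adaptation, but does not rest that on this table. The other is that the trial cannot compare background therapy at all. The unaffected rows, trough levels, ATC summaries and time-to-additional-therapy summary do part of that work. The primary analysis and the type I error are untouched.

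The conclusion assumes that no equivalence rule sits in redacted text; part of SAP section 16 and all of 14.5 are not visible.

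**What to change.** In SAP 12.1 and 12.2:

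1. Report cumulative dose and dose per day for each drug, by arm and interval.
2. Pre-specify a corticosteroid equivalent before summing steroids. State how MMF or equivalent in the protocol synopsis is to be read, and give the conversion if a dose equivalent is meant.
3. Drop the overall mg total and every mixed-drug total without a stated conversion.
4. Keep the per-class Fisher tests.
5. Add a by-arm tabulation of within-class switches and dose increases after randomization.
6. List the change from the protocol synopsis in SAP section 16, if it is not already in the redacted part.

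The dosages and the dates of start, stop and change are already recorded in the eCRF, so no new data are needed. The cost is a conversion list agreed before database lock, some SAP wording and revised table shells.

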### 12.2 Other Immunosuppressants

Other immunosuppressants refer to all the immunosuppressive therapies that are not classified as maintenance regimen as described in section 12.1 (but meet the conditions reported in section 12). Other immunosuppressive therapies will be coded by Anatomical Therapeutic Code (ATC) codes, and will be summarized by treatment group for SAF, FAS and PPS.

All other immunosuppressants administered from the day of randomization will be evaluated. The number (%) of patients taking any other immunosuppressants will be provided overall and for each ATC code.

The same summary statistics for cumulative dose and for exposure as described in section 12.1 will be provided.

#### 13 Prior and concomitant medications

Prior medications are those medications taken prior to randomization with a stop date and time prior to the randomization date/time (standard definition of prior/concomitant medications considers the first dose of study treatment but, as in this study SOC group won't have any first dose date, randomization date will be considered instead).

Concomitant medications are those medications with a start date and time on or after the randomization date/time, or those with a start date and time before the randomization date/time

Final Version 5.0 Page 37 of 76

and either a stop date and time on or after the study randomization or are ongoing at the end of the study.

Prior and concomitant medications will be summarized by ATC codes and listed for FAS. Prior/concomitant medications will be coded using the WHO-DD classification system and grouped by drug class and PT.

#### 14 EFFICACY

For the efficacy analysis, the adequacy of the model assumptions will be checked, and if it is found that these are inadequate then alternative approaches may be performed.

For all variables assumed to be normally distributed, the conditional studentized residuals from this model will be tested using the Shapiro-Wilk test. If the assumption of normality of these residuals is violated, then a log-transformed model will be fitted. The need for a possible log transformation of these variables will be investigated prior to unblinding by assessing the model residuals without a treatment term. Where data are transformed for analysis, back transformation will be applied for the presentation of results. Presentation of the tables will be amended as needed for this, with the addition of an explanatory footnote.

Classification and imputation of missing data will be completed prior to any transformation of the data for analysis.

As a general remark for all efficacy endpoints based on spirometry data, values collected at 1h and 4h post dose will not be used for any efficacy analyses as they are collected only for safety evaluations.

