#### 14.1 PRIMARY EFFICACY ANALYSIS

## 14.1.1 Analysis Population and Estimand

The primary endpoints will be analyzed using a "composite strategy" (International Conference on Harmonization (ICH) guideline E9 addendum on estimands and sensitivity analysis in clinical trials to the guideline on statistical principles for clinical trials). The estimand is defined by the following:

- Population: adult recipients of a double pulmonary allograft with clinically defined BOS, matching the inclusion and exclusion protocol criteria.
- Variable: FEV1 data at Week 48 (visit 9) collected from the onsite CO spirometer (data collected with the CO home spirometer will be used for supplementary analyses).
   Only accepted over-reader best FEV1 data for the session from CO will be used for analysis; data will not be re-derived.

Final Version 5.0 Page 38 of 76

Intercurrent events: After IEs such as stopping treatment with L-CsA, augmentation of SoC therapy, etc.,  $FEV_1$  measurements will still be collected and used in the analysis. In case of IEs preventing the use of  $FEV_1$  measurements, i.e. death and re-transplantation, the  $FEV_1$  will be imputed as treatment failure:  $FEV_1$  equal to zero for all visits subsequent the event.

Rejected spirometries are those that did not meet the American Thoracic Society criteria; if rejected, then they would be re-done but there may be cases where they are rejected twice and resulting in missing data. Rejected spirometry is not an indicator of a better/worse outcome and can be assumed to be MAR.

• Population-level summary: difference in mean change from baseline in the FEV1 at week 48 between treatment groups.

Table 5 summarizes the statistical approaches for handling IEs and missing data.

Final Version 5.0 Page 39 of 76

Table 5: Summary of strategies for Intercurrent Events and Missing data.

	Statistical analysis					
Type of IEs	Primary analysis (section 14.1.3)	Missing data not at random (MNAR) (section 14.2.1)	"While on treatment" strategy (for COVID-19) (section 14.3.3.3)	"While on treatment" strategy (section 14.3.5)	Trimmed Means (section 14.3.6)	
Death	The FEV 1 value will be	The FEV 1 value will be imputed equal to zero.	Not applicable.	Not applicable.	The FEV 1 value will be	

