### 14.1.3 Analysis Model

The primary efficacy analysis will be carried out using a LMM for repeated measurements, using all observed available  $FEV_1$  measurements. In case of death or re-transplantation events,  $FEV_1$  will be imputed as zero at each nominal day post event.

The dependent variables are the absolute change from baseline of FEV1 measurements at visit 2 (i.e., the first post-baseline visit) through visit 9 (Week 48). For the definition of baseline FEV1 please refer to section 8.1.1.

A flexible and robust model will be chosen for the random part of the LMM according to a prespecified stepwise procedure (see next section). The fixed part of the LMM is specified as follows: the model will contain (except from the intercept) time cubic splines, treatment, the interactions of time splines by treatment, baseline FEV1, the interactions of time splines with the baseline FEV1, region (North America versus all other countries together), age (< 55 versus  $\ge 55$  years), and use of azithromycin at randomization (i.e. Baseline, Visit 1).

The primary efficacy parameter will be estimated from the model by the adjusted difference between treatment groups in mean FEV1 change from baseline after 48 weeks. The p-value for the null hypothesis of no difference and a two-sided 95% confidence interval for the difference will be provided.

Superiority of L-CsA will be demonstrated by a statistically significant result (defined as p<0.025, one-sided) in favor of the L-CsA plus SoC treatment compared to SoC alone.

The above comparison between treatment groups at all the other visits (2-8) will also be presented.

A figure of observed mean change from baseline and standard errors at each visit, by treatment group will be presented. A figure with adjusted mean changes from baseline at each visit by treatment group derived from the LMM will be provided.

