#### 14.2.5 ANCOVA

The population-level summary for the variable will be altered. An ANCOVA model will be performed on the changes from baseline in FEV1 to Week 48, using the same stratification factors and the same covariates described for the LMM for the primary efficacy analysis (except for time factors). In case of death or re-transplantation events, FEV1 will be imputed as zero at each nominal day post event.

In case of violation of the normality assumption even after log transformation (section 14), then rank transformation will be applied to normalize the data. The same ANCOVA model will be applied to the rank-transformed data.

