#### 14.6 SUBGROUP ANALYSES

Analyses of primary endpoints will be performed on the following subgroups of patients:

- Age class (<55 years, ≥55 years),

- Gender (female, male, undifferentiated),
- Region (North America, all other countries together),
- Severity of disease, defined by:
  - % of baseline FEV₁ over personal best FEV₁ post-transplant (baseline FEV₁ >80%,
     >65–80%,
     >50–65%,
     and ≤50% of personal best FEV₁ post-transplant),
  - baseline FEV1 % of predicted (<70%, ≥ 70%),

  - baseline FEV1/FVC ratio (< 0.7, ≥ 0.7),

  - BLAD at baseline (Yes, No);
- Race (American Indian or Alaskan Native, Asian, Black or African American, Native Hawaiian or Other Pacific Islander, White, Other),
- Use of azithromycin at randomization (Yes/No).

Final Version 5.0 Page 59 of 76

Subgroup levels may be pooled to have an adequate number ( $\geq 10$ ) of patients per strata to perform the analysis. Decision on pooling will be taken during the blinded DRM, before data base lock.

Within each subgroup level, descriptive analyses (section 8.1) will be performed on:

- FEV1,
- FEV1/FVC,
- Time to Progression of BOS.

FEV1 and FEV1/FVC change from baseline will be compared using a two-sample t-test (assuming unequal variances) or, if the required assumptions are not met, a two-sample Mann–Whitney U test.

Comparison of time to progression of BOS curves among treatments will be performed with the log-rank test.

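### The SAP's rule to fit a log-transformed model after a failed normality test reaches the primary FEV1 analysis, where the logarithm cannot be computed

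*SAP*

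**What the plan says.** The introduction to SAP Section 14 applies to every efficacy variable assumed to be normal. Conditional studentized residuals go to a Shapiro-Wilk test, for which no significance level is given, and the consequence is stated: "If the assumption of normality of these residuals is violated, then a log-transformed model will be fitted". On timing: "The need for a possible log transformation of these variables will be investigated prior to unblinding by assessing the model residuals without a treatment term". On order: "Classification and imputation of missing data will be completed prior to any transformation of the data for analysis". The same introduction allows unspecified alternative approaches if model assumptions prove inadequate.

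The primary analysis is described as follows.

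- **Outcome (14.1.3):** "The dependent variables are the absolute change from baseline of" FEV1 at visits 2 to 9.
- **Death or re-transplantation (14.1.3):** FEV1 "will be imputed as zero at each nominal day post event".
- **Estimand (14.1.1):** "Population-level summary: difference in mean change from baseline in the" FEV1 at Week 48, compared between arms.

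Two other sections deal with non-normality of the same change variable. For the sensitivity ANCOVA, 14.2.5 says: "In case of violation of the normality assumption even after log transformation (section 14), then rank transformation will be applied to normalize the data". For subgroups, 14.6 uses a t-test "or, if the required assumptions are not met", a Mann-Whitney test, with no log step.

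**The concern.** The general rule is mandatory in form and covers the primary LMM. Conditional residuals belong to a random-effects model, and 14.1.3 to 14.1.5 contain no exemption. Section 14.2.5 shows that the log step is meant for change in FEV1. Yet neither candidate variable can be logged for all rows, and the visible text gives no offset, no log-ratio and no rule for zeros.

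The trigger is not remote. A patient whose FEV1 drops to 0 L produces just the outlying residuals that Shapiro-Wilk detects. The zero imputation came in with SAP version 5.0 (Section 4), after the version that added the rank fallback behind the log step, and the two were not reconciled.

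If the test fails, someone must settle the confirmatory model outside the plan. The available repairs differ greatly in their chance of success. One of them, omitting the zeros, removes the events that the composite strategy was adopted to count. A back-transformed log model would also estimate a ratio rather than the declared difference in mean change.

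**Working it through.** **Plan's own figure.** SAP 8.2 assumes a 0.2 L difference, SD 0.35 L and one-sided alpha 0.025. The exact t-test needs 49.05, so 50 per arm, with 80.8% power at 50. This reproduces. The point does not rest on it, but the same effect and SD are used below.

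**1. Can the log be taken?**

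- log(change): undefined for any change of zero or less.
- log(FEV1): log(0) is minus infinity for every imputed row.
- log(FEV1/baseline): log(0/baseline) is again minus infinity.

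Imputation precedes transformation, so the zeros are present when the log is applied.

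**2. How many changes are zero or negative?** Protocol 7.1.4 gives slopes of -0.008 and -0.045 L/month from the earlier treatment study. Over 48 weeks (11.04 months) these become -0.088 and -0.497 L. With SD 0.35 L:

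- L-CsA: Phi(0.088/0.35) = 0.60
- SoC: Phi(0.497/0.35) = 0.92

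**3. How often would the test fail?** Assumptions: 169 patients (SAP 8.2), 8 visits, about 1,130 rows; baseline 2.0 L (SD 0.6); Week 48 mean change -0.30 L on SoC and -0.10 L on L-CsA; survivor SD 0.35 L; measurement SD 0.10 L; random-walk course; 25% dropout; uniform event times. The model was the spline LMM without treatment terms, with random intercept, t, t² and t³. The test level was taken as 5%, with 300 to 400 trials per row.

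| Imputed events in the trial | Shapiro-Wilk rejects |
|---|---|
| 0 | 4.3% |
| 1 | 81.2% |
| 2 | 95.7% |
| 3 | 98.7% |

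With random intercept and slope only, the rates for 0, 1 and 2 events are 7.7%, 82.3% and 95.3%.

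**4. Overall trigger probability.** The documents give no 48-week event rate, so r is assumed. P(at least one event) = 1 - (1 - r)^169. The overall probability weights the step 3 rates by the binomial probabilities, using 98.7% for three or more events.

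| r | P(at least one event) | Overall trigger |
|---|---|---|
| 0.5% | 57% | 51% |
| 1% | 82% | 75% |
| 2% | 97% | 93% |

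For r = 0.5%, the probabilities of 0, 1, 2 and 3 or more events are 0.429, 0.364, 0.154 and 0.054. The sum is 0.043×0.429 + 0.812×0.364 + 0.957×0.154 + 0.987×0.054 = 0.51.

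**5. Does the choice of repair matter?** Week 48 ANCOVA with the same means and SD, a true 0.2 L effect, 25% missing, one-sided 0.025, 3,000 trials. The last column is log FEV1 with the zeros omitted. The offsets and the omission are examples; the SAP proposes none of them.

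| Events | Litres | log(FEV1+1) | log(FEV1+0.1) | log, zeros dropped |
|---|---|---|---|---|
| None | 87.9% | 86.7% | 83.4% | 82.4% |
| 1 per arm | 76.3% | 62.8% | 22.1% | 82.7% |
| 2 per arm | 64.3% | 39.6% | 4.1% | 81.9% |
| 3 SoC, 1 L-CsA | 90.0% | 85.5% | 61.7% | 82.3% |

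Separate repeats of the two-per-arm case gave 63-64%, 40-42%, 5% and 79-80%.

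**The case against.** The best reply is that the primary model is fixed elsewhere. SAP 8.3.4 settles on the LMM, and 14.1.3 to 14.1.5 specify its outcome, splines, random effects and success criterion without mentioning a log. A specific section usually governs a general preamble. The preamble is also soft in places: it speaks of a possible transformation, allows other approaches, and makes the check before unblinding in a model without treatment. The program code and Table 8 are redacted, so an offset there cannot be excluded. Finally, the sizes depend on assumed event rates, and Protocol 15.2.3.1 expects these events to be rare.

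Some of this stands. The blinded check does limit a results-driven choice. The 60% and 92% shares matter only if signed change is logged; log FEV1 is defined for every positive observed value and breaks only on the imputed zeros. The power figures come from a Week 48 ANCOVA, not the LMM. The last column of the step 5 table mixes the log scale with the omission of zeros, so its gap from the litre column is not the effect of omission alone.

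None of this gives the rule a computable form. Checking early fixes when to decide, not what to fit. The permission for alternatives names no model. The rank fallback serves only the sensitivity ANCOVA, and only after the log step. The specific-over-general reading may well be what was intended, but the SAP does not say so. As to rarity, one event among 169 patients is enough. In the earlier treatment study 16 of 21 patients were no longer alive at five years (Protocol 7.1.4); this is not a 48-week rate, but it makes at least one event plausible.

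**Conclusion.** The concern holds: the rule is wrong as written for the primary analysis. That conclusion needs only the SAP's text and the domain of the logarithm. How likely the rule is to be triggered (about 51% to 93% at event rates of 0.5% to 2%) depends on the assumed 5% test level, the event rates and the simulated course of FEV1. How much the repair matters (power from 4% to 82% with two events per arm) depends on the example repairs and the Week 48 model. With no events the four columns lie between 82% and 88%, so the damage comes from the zeros. Because the gap concerns the confirmatory analysis, it should be closed before database lock.

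**What to change.** Make two changes to the SAP wording:

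1. In Section 14, state that the primary LMM on change in FEV1 in litres is the analysis of record whatever the residual test shows.
2. Remove the log step for all analyses of change in FEV1, including 14.2.5. Non-normality there should lead directly to the rank-transformed ANCOVA, as a sensitivity analysis read alongside the permutation-based trimmed-mean analysis already planned in 14.3.6.

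This keeps the declared difference in mean change and the composite handling of death and re-transplantation. It costs two sentences before database lock, with no new data and no new analysis.
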